## 6. STUDY VACCINE

### 6.1 Study vaccines and antimalarial medications

The Investigational Brochure (IB) for RTS,S/AS01E will be provided to the ethical and regulatory review committees. The candidate RTS,S/AS01 vaccine to be used has been developed and manufactured by GSK Biologicals. The vaccine is labelled and packed according to applicable regulatory requirements.

RTS,S antigen is a lyophilized pellet containing 25 µg of RTS,S per vial. The pellet is reconstituted with adjuvant in liquid form and 0.5 mL of reconstituted vaccine contains 25 µg RTS,S. The AS01E adjuvant contains 25 µg of MPL®, 25 µg QS21 (QS21 is a triterpene glycoside purified from the bark of *Quillaja saponaria*) in a suspension of liposomes in phosphate buffered saline per 0.5 mL and is presented in 3 mL monodose vials. The presentation of the reconstituted RTS,S/AS01E candidate malaria vaccine is an opalescent liquid. RTS,S/AS01E will be provided by GSK and sent directly to the study sites in Burkina Faso and Mali. A single dose consists of 0.5 ml of RTS,S/AS01E final preparation. After reconstitution, the vaccine is administered by slow intramuscular injection, using a fresh 25G needle with length of one inch (25 mm), into the left deltoid. Vaccine is injected within four hours of reconstitution (storage at +2°C to +8°C).

Tetanus toxoid vaccine will be procured by LSHTM from the Serum Institute of India and sent directly to the study sites in Burkina Faso and Mali. Tetanus vaccine is provided in a 0.5ml single dose vial containing tetanus toxoid ≥ 40 IU adsorbed on Aluminium Phosphate ≤ 1.25 mg. Due to the impact of the COVID-19 pandemic, it may not be possible to air freight the tetanus toxoid vaccine ordered from the Serum Institute of India to Burkina Faso and Mali in time for this to be administered in June 2020. In this situation, tetanus/diphtheria toxoids vaccine will be provided by the national infant immunization programmes of Burkina Faso and Mali from the stock utilized routinely in their national immunization programmes and obtained from recognized manufacturers through UNICEF. The vaccine contains an aluminum phosphate adjuvant. Both vaccines are administered by slow intramuscular injection into the deltoid muscle.

#### 6.1.1 Product storage and handling

All vaccine vials/pre-filled syringes (RTS,S) and AS01E adjuvant and the tetanus or tetanus/diphtheria toxoids vaccine will be stored in a refrigerator (+2°C to +8°C) and not frozen. All vaccine/adjuvant/water for injection vials will be stored in a safe place with no access for unauthorized personnel. The storage temperature will be monitored continuously with calibrated temperature monitoring device(s) and recorded according to SOPs at the investigator's site. An alarm system and a back-up refrigerator will be available in case of power failure/breakdown. GSK and the study monitor will be contacted if the cold chain is broken, for example if vaccines become frozen or refrigeration fails.

GSK will manage temperature deviations during the primary shipment until the reception at the clinical trials site. Temperature excursions are the responsibility of the sponsor upon receipt of the RTS,S/AS01E study product. Any temperature excursion outside the range of 0.0 to +8.0°C (for +2 to +8°C/+36 to +46°F label storage condition) will be reported to the sponsor (LSTMH) and GSK. In case of temperature excursion below +2.0°C down to 0.0°C there will be no need to report this deviation but adequate actions will be taken to restore the +2 to +8°C/+36 to +46°F label storage temperature conditions.

Anti-malarial medications will be stored below 30°C in designated storage rooms.

### **6.1.2 Preparation**

For this study, the commercial presentation of RTS,S/AS01E will be used, i.e. a two-dose glass vial of lyophilized RTS,S antigen (50 µg) to be reconstituted with a two-dose glass vial of AS01E Adjuvant System (1.0 ml). The final product for administration will be prepared by reconstitution of the lyophilized antigen with the liquid adjuvant. From the reconstituted vaccine vial, 0.5 mL will be administered for RTS,S/AS01E full doses. All vials of vaccine provided in this study are intended for single use only. Loading of syringes with RTS,S/AS01E or tetanus or tetanus/diphtheria toxoids, and masking syringes with tape to disguise their content, will be done by a person who takes no further part in the trial. Vaccines will be administered by a nurse or other category of health worker trained to give vaccines.

### **6.1.3 Route of administration**

The route of administration for both RTS,S/AS01E and tetanus or tetanus/diphtheria toxoid will be by the intramuscular route to the deltoid muscle

SP and AQ will be administered orally according to the dosages recommended by the National Malaria Control Programme.

## **6.2 Study vaccine accountability procedures**

The study vaccines will be distributed to and maintained by the pharmacies in Burkina Faso and Mali and will include accounts of the amount of product shipped, documentation of adequate and safe handling and use, temperature logs for vaccine product and plans for returning or destroying unused product with the exception of any tetanus toxoid which, with permission of the sponsor, may be donated to the respective national EPI programmes.

## **7. STUDY INTERVENTIONS**

### **7.1 Insecticide-treated bednets (LLIN)**

At the start of extension study, all child in the trial who can be identified will be issued with a new LLIN regardless of whether or not their family consents for them to remain in the extension study.

### **7.2 The RTS,S/AS01E vaccine**

As described previously, the RTS,S/AS01E vaccine is a virus like particle (VLP) composed of the CSP protein of *P. falciparum* and HBsAg which is given with the adjuvant, AS01E. The vaccine may cause local side effects such as pain and redness at the site of vaccination in approximately 20% of recipients and minor systemic effects such as drowsiness and irritability are sometimes observed following vaccination. Fever post vaccination occurs in about 10% of children and febrile convulsions occurred in about 1% of

5-17 month old recipients enrolled in the phase 3 trial [3] but no persistent neurological effects were recorded. The main safety issues related to administration of RTS,S/AS01E during the phase 3 trial were a statistically significant increase in meningitis in children given the vaccine at the age of 5-17 months and an apparent increase in mortality in female vaccine recipients. However, during the first three years of the current trial, only five cases of febrile convulsion have been reported among the approximately 4,000 children who have received three priming and two booster doses of RTS,AS01 or control vaccine and no proven case of meningitis has been detected. Following a fifth dose of RTS,S/AS01E given in 2019, no increase in reported local or systemic side effects compared to previous vaccine doses was noted. To ensure that minor local and systemic adverse events, such as a reaction at the vaccine site or fever, are not enhanced following repeated doses of RTS,S, adverse events during the first seven days after vaccination will be recorded in a sub-set of children. SAEs will be recorded in all children throughout the period of the trial, as described below in Section 8 and Appendix 2.

### **7.3 Comparator vaccines**

A single dose of tetanus or tetanus/diphtheria toxoid will be used as the comparator vaccine for children in SMC alone group in the first and second years of the extension study. A booster dose of tetanus or tetanus/diphtheria/ pertussis vaccine at about the age of 18 months is recommended by WHO but is rarely given so that a majority of the children in the control group will receive some benefit that they would not have obtained had they not been enrolled in the trial. Tetanus or tetanus/diphtheria toxoid vaccine may produce some minor local and systemic effects but is very safe.

### **7.4 Vaccine administration**

Vaccination will be undertaken during a mass campaign lasting one to two weeks during June 2021 and June 2022. Children with a minor illness, such as mild diarrhea or a mild upper respiratory infection without fever, at the time they present for vaccination will be vaccinated. Those with recorded fever and/or other features of a more serious acute illness will not be vaccinated but will be treated for their illness and vaccinated when this has resolved. Children who miss the mass vaccination programme but who attend any of the subsequent rounds of SMC administration will be offered vaccination at that time.

### **7.5 Seasonal Malaria Chemoprevention (SMC)**

Four or five courses of SMC with SP+AQ will be given at monthly intervals during the malaria transmission season to children in the SMC alone and SMC +RTS,S/AS01E groups. A course of SMC for children aged over the age of one year comprises a single treatment of SP (500mg/25 mg) and AQ 150mg on day 1 and AQ 150mg on days 2 and 3. SP and AQ and matching placebo will be obtained from Guilin Pharamceuticals, Shanghai, Co, a GMP-certified supplier. All treatments will be given under observation. SP can cause Stevens-Johnson syndrome, but this side effect has been seen very rarely when SP has been used for either intermittent preventive treatment of malaria in pregnancy or SMC. Amodiaquine is bitter and may cause vomiting but serious side effects, which include liver damage and neurological side effects, are very rare. SMC with SP+AQ has proved to be very safe. A study conducted in Senegal in which the consequence of administration of 800,000 doses of SMC with SP+AQ were followed carefully identified only three serious potentially drug related adverse effects (two cases of hepatic damage and one extra-pyramidal syndrome) [11]. Enhanced pharmaco- vigilance in 7 countries participating in the ACCESS-SMC project funded by UNITAID, through which approximately 15 and 30

million treatment courses were administered in 2015 and 2016, respectively, has confirmed that SMC with SP+AQ is very safe.

SMC drugs will pre-packed by a pharmacist, who takes no further part in the trial, in re-sealable envelopes bearing the child's unique number and containing tablets for the four cycles of treatment required for one malaria transmission season. Treatment with each dose of SMC is given by trained, paid volunteers at a central point in each study community under observation. Study children will be given an updated identity card containing their photo, study identity number and date of birth. At the time of vaccination and/or SMC administration, a child's photo ID card is scanned to ensure that the child is given the allocated intervention. Home visits are made to children who miss treatment on the designated day and their parents/guardians are asked if they would still like their child to receive SMC. If they agree, treatment is given at home.

The interventions that children in each study group will receive during the extension period are summarised in Table 1.

**Table.1** Summary of the interventions that will be given to study children in each study group during the extension study

|             | Group1 (SMC)  | Group2 (RTSS)                                     | Group3 (RTSS+SMC)                 |
|-------------|--|--|--|
| 2020 |  |  |  |
| June        | Tetanus or
Tetanus/diphtheria
toxoids x 1
SMC x 4 | RTSS/AS01 x 1  | RTSS/AS01 x 1                            |
| July -Oct   |  | SMC placebo x 4  | SMC x 4                                  |
| 2021 |  |  |  |
| June        | Tetanus or
Tetanus/diphtheria
toxoids x 1            | RTSS/AS01 x 1  | RTSS/AS01 x 1                            |
| July -Nov   | SMC x 4 (Mali)
SMC x 5 (Burkina Faso)                   | SMC placebo x 4 (Mali)
SMC placebo x 5 (Burkina Faso) | SMC x 4 (Mali)
SMC x 5 (Burkina Faso) |

(SMC or placebo is given at monthly intervals on four or five (Burkina Faso 2021) occasions during the malaria transmission season.)

## 7.6 Follow-up and measurement of endpoints

The following follow-up procedures required to measure the study outcomes will be undertaken.

### 7.6.1 Passive surveillance for uncomplicated and severe malaria.

In each country, project staff are based in the district hospital and in the main dispensaries that serve the study communities and, working with health service staff, they will be responsible for identifying and documenting all cases of malaria who present to these facilities. In Mali, cases of uncomplicated malaria may be treated by community health workers who have been taught to diagnose malaria with a RDT and to treat RDT positive cases. Cases of suspected malaria (fever, history of fever within 48 hours

or any other symptom/sign suggestive of malaria) will be managed on the basis of their RDT result but blood films and filter paper strips will be obtained from all these cases for subsequent confirmation of the malaria diagnosis.

### **7.6.2 Active surveillance for malaria**

Each month throughout the study period, 96 randomly selected children (32 from each arm of the study) in each country will be visited at home, their temperature measured and a blood film collected for subsequent detection of asymptomatic parasitaemia. Any child who is febrile or who has other features suggestive of a diagnosis of malaria at the time of the home visit will have an RDT done and if this is positive s/he will be treated with artemether/lumefantrine. This activity is suspended due to COVID-19.

### **7.6.3 Prevalence of malaria parasitaemia and anaemia.**

A survey of all study children will be undertaken approximately one month after the last round of SMC administration at the end of each malaria transmission season. Temperature will be measured and any child who is febrile or who has other features suggestive of a diagnosis of malaria will have an RDT done; those who are positive will be treated with artemether/lumefantrine. Finger prick blood samples will be collected for preparing blood slides and filter paper blood spots. The prevalence of parasitaemia, including the presence of gametocytes, will be detected by microscopy.

### **7.6.4 Evaluation of mutations in the *P.falciparum* csp gene**

Because the efficacy of RTS,S/AS01E has been shown to be influenced by the occurrence of mutations in the *csp* gene [17] this will be measured in samples obtained from children with clinical episodes of malaria and in children with parasitaemia at the cross-sectional survey.

### **7.6.5 Immune response to the RTS,S/AS01E vaccine**

Blood samples (4ml) will be collected from approximately 160 children in each of the groups (80 per country) who received RTS,S/AS01E and from approximately 20 children in the SMC alone group prior to and one month after administration of the third and fourth booster doses of RTS,SD/AS01 for measurement of anti-CSP antibodies. Children will be selected randomly for each blood draw.

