### **10.3.2 Sample size for the serological assays**

For the analysis of the serological response to RTS,S/AS01E, comparisons will be made between mean anti-CSP antibody titres pre and post the sixth and seventh RTS,S/AS01E doses. Based on the standard deviations in antibody titres observed in children enrolled in the RTS,S/AS01E phase 2 and phase 3 trials, inclusion of around 160 individuals in each group (pre and post vaccination at each of the two time points) will give a study with approximately 80% power to detect a difference of 25% - 30% in mean titre between groups.

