### **2.4 The antibody response to sixth and seventh doses of the RTS,S/AS01E vaccine**

- 2.4.1 The *Plasmodium falciparum* anti-CSP antibody titre before and after the sixth and seventh doses (third and fourth 'booster' doses) of the RTS,S/AS01E malaria vaccine.
- 2.4.2 The association between the magnitude of the anti-CSP antibody response to the sixth and seventh doses of the RTS,S/AS01E vaccine and the risk of malaria during the subsequent malaria transmission season.

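### Anti-CSP children appear to be re-selected for each blood draw, leaving pre- and post-dose titres largely unpaired: means stay comparable, but precision is lost and few children have an individual rise

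*Combined protocol and SAP*

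**What the plan says.** Protocol Section 7.6.5 takes 4 ml samples from "approximately 160 children in each of the groups (80 per country) who received RTS,S/AS01E", plus about 20 children in the SMC-alone group, "prior to and one month after administration of the third and fourth booster doses". It then says: "Children will be selected randomly for each blood draw".

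Protocol Section 10.3.2 describes the analysis: "comparisons will be made between mean anti-CSP antibody titres pre and post the sixth and seventh RTS,S/AS01E doses". Its sample size is "inclusion of around 160 individuals in each group (pre and post vaccination at each of the two time points"), said to give "approximately 80% power to detect a difference of 25% - 30% in mean titre between groups". The variability is described only as "Based on the standard deviations in antibody titres observed in children enrolled in the RTS,S/AS01E phase 2 and phase 3 trials". No SD, scale, significance level or within-child correlation is given.

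The SAP (Secondary Endpoints, 2.4) lists two outcomes. Outcome 2.4.1 is the titre before and after doses six and seven. Outcome 2.4.2 is "The association between the magnitude of the anti-CSP antibody response to the sixth and seventh doses" and later malaria risk. Magnitude is not defined, and the SAP's statistical methods for secondary endpoints name no model for antibody titres.

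**The concern.** A pre-dose sample and a one-month post-dose sample are two blood draws. If children are selected afresh for each, few will be in both samples. Two things follow.

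- The pre/post comparison carries the full between-child variance twice. Sampling the same children would remove the part of that variance the two measurements share.
- Most sampled children have either a pre-dose or a post-dose value. These children have already had five doses, so a post-dose titre combines residual antibody with the response to the new dose. Separating the two in 2.4.2, by adjusting for pre-dose titre or by using fold-rise, needs both values from the same child.

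At stake are the precision of the booster-response estimate and what 2.4.2 can say. No primary, non-inferiority or safety conclusion depends on either.

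**Working it through.** **1. The plan's own figure.** Inputs from Section 10.3.2: n = 160 per group, power about 80%, difference 25–30%. Assumed: two-sided 5%, log-titre scale, two independent samples. The detectable log ratio is

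d = (1.960 + 0.842) × SD × √(2/160) = 0.313 × SD.

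With no SD in the documents, the figure cannot be checked independently; one can only solve for the SD.

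- 25% rise: SD = ln(1.25)/0.313 = 0.71 on the ln scale (0.31 on log10).
- 30% rise: SD = ln(1.30)/0.313 = 0.84 (0.36 on log10).
- If the difference is a 25–30% fall instead, the ln SD is 0.92–1.14.

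Across assumed ln SDs of 0.6 to 1.2, the detectable rise runs from 20.7% to 45.6%. The stated figure is therefore compatible with an unpaired calculation but does not prove one.

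**2. The same 160 children sampled twice.** The SD of the within-child difference is SD × √(2(1−ρ)), so d is multiplied by √(1−ρ). The confidence interval for the log ratio narrows by the same factor, whatever the SD. The correlations ρ are assumptions.

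| ρ | √(1−ρ) | Detectable rise (25% unpaired) | Detectable rise (30% unpaired) | Power at 160 pairs for the unpaired difference | Pairs for 80% power |
|---|---|---|---|---|---|
| 0 | 1.00 | 25.0% | 30.0% | 80.0% | 161 |
| 0.3 | 0.84 | 20.5% | 24.5% | 91.8% | 113 |
| 0.5 | 0.71 | 17.1% | 20.4% | 97.7% | 81 |
| 0.7 | 0.55 | 13.0% | 15.5% | 99.9% | 49 |

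**3. Chance overlap if each draw is fresh.** Two independent random samples of n from N children share n²/N on average.

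- 2020: about 4,800 children enter the extension (Protocol Section 10.2), so N = 1,600 per group and the overlap is 160²/1,600 = 16, or 10% of those sampled. With the consented totals in the SAP, N = (2,410 + 2,624)/3 = 1,678 and the overlap is about 15.
- 2021: 3,860 of 5,920 are not eligible (SAP, Analyses in individual years), so N = 2,060/3 = 687 before attrition and the overlap is about 37 (23%). Scaling by 5,034/5,920 for attrition gives N = 584 and about 44 (27%).

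**4. What 2.4.2 still has.** Each post-dose draw gives about 160 post-dose titres per RTS,S group, or 320 over both. At 200 episodes per 1,000 child-years that is 320 × 0.2 = 64 episodes in a year. The detectable hazard ratio per SD of titre, at 80% power, is about exp(−2.80/√64) = 0.70. In one group alone (32 episodes) it is 0.61. This is a simple approximation that ignores repeat episodes and differing rates between groups.

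**The case against.** A reader might infer that 2.4.2 cannot be answered at all. The documents do not support that. Magnitude is not defined as a rise; every child in a post-dose sample has a titre that can be linked to that child's surveillance data; and Protocol Section 2.1 ties protection to high titres, not to fold-rise. For the same reason, fold-rise should not replace titre in 2.4.2: a child with a high pre-dose titre can have a small rise and still end with a high titre.

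Nor does the literal reading make the design invalid. Independent random samples give unbiased mean titres before and after each dose, which is what 2.4.1 asks for. Drawing afresh also spares most children a second venepuncture. The loss is one of efficiency, not bias.

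Unpaired sampling is itself an inference. The opening sentence of Section 7.6.5 can be read as the same children sampled before and after, with the random selection applying to each pre/post pair. The parenthesis in Section 10.3.2 could describe when the 160 are sampled. That reading is possible but less natural: Section 10.3.2 speaks of a difference between groups, names pre and post where it defines them, and uses no within-child correlation. No passage states either design.

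Finally, the size of the gain rests on a back-solved SD and assumed correlations, and there is no gain if sampling is already paired. That is right, and the verdict is limited accordingly.

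**Conclusion.** The point holds as a loss of precision and of individual change, conditional on the literal reading of Section 7.6.5. On that reading, only about 10% of sampled children per RTS,S group would have both samples in 2020, and about 23–27% in 2021. The mean comparison in 2.4.1 is valid but less precise than the same number of assays could make it: the detectable rise is 25–30% instead of about 20.5–24.5%, 17–20% or 13–15.5% at correlations of 0.3, 0.5 or 0.7. Outcome 2.4.2 remains answerable with post-dose titre, but for most children without adjustment for pre-dose titre and without fold-rise.

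The assumptions are two-sided 5%, a log scale, an unpaired original calculation, equal group sizes and the stated correlations. The weight is moderate: the SAP lists these outcomes as secondary, and Protocol Section 4.2.3 lists anti-CSP concentrations as exploratory. The change is nonetheless inexpensive for what it gains.

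**What to change.** **Sampling.** Select about 160 children per RTS,S group at random once per booster year, and take both the pre-dose and the one-month post-dose sample from those children.

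**Analysis.** Analyse 2.4.1 as a within-child log ratio. For 2.4.2, define magnitude as log post-dose titre, with pre-dose titre as a covariate or fold-rise as a supplementary analysis. State the SD, scale, significance level and assumed correlation in Section 10.3.2, and name the models for both outcomes in the SAP.

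**Cost.** The number of samples and assays is unchanged. Each selected child gives two 4 ml draws in that year instead of one, and fewer distinct children are sampled. A child who misses the second draw leaves an incomplete pair.

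**If sampling is already complete.** This is likely: the SAP describes the 2020 and 2021 vaccinations in the past tense, and Protocol Section 12 gives figures as of 17 December 2021. The remaining step is then to state, before the randomisation code is broken, whether samples were paired, to analyse any pairs as pairs, and to fix the definition of magnitude. This costs only text.
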